6 STUDY INTERVENTION(S) OR EXPERIMENTAL MANIPULATION(S)

6.1 STUDY INTERVENTION(S) OR EXPERIMENTAL MANIPULATION(S) ADMINISTRATION

6.1.1 STUDY INTERVENTION OR EXPERIMENTAL MANIPULATION DESCRIPTION

[figure not shown]
We will study two types of facilitators (messaging and financial incentives) and evaluate the heterogeneity of treatment response based on the characteristics of those tested. We will conduct a 2 x 2 (messaging x financial incentive) factorial design that stratifies on social and behavioral determinants collected as part of an initial survey. We have been studying ways to identify powerful incentives for repeated health behaviors. We have found that providing at-risk incentives that can be insured with *repeat* health behavior outperforms direct cash payments of the same expected value. Individuals were 70% more likely to return to a health screening when insuring against losing a baseline incentive than they were when paid cash ($p < 0.01$).⁴ In addition, in a recent study we showed that disadvantaged patients at a federally-qualified health center were more likely to repeat a health behavior twice each week over 12 weeks when repetition was insuring against losing a weekly incentive than if they were paid equivalently in cash.

Messaging (Factor 1): We will develop simple messaging that frames the decision to test in terms of either: (i) *family risk*, or, (ii) *personal risk*. These methods will be piloted, but will be of the form "Antibody testing will help you understand your family's risk of getting COVID-19"; and, "Antibody testing will help you understand your risk of getting COVID-19". Family risk framing may engender concern for loved ones. It may also make it easier to mentally simulate family burdens with COVID-19 such as knowing how several people in the family becoming sick could adversely affect the lives of everyone in the family. We hypothesize that the family framing will result in greater uptake of testing and greater repeat testing.

Incentives (Factor 2): We have been studying incentives for repeat testing since 2015.⁴ We have found that low-income persons respond better to insuring at-risk rewards with repeat behavior than they do to cash payment.⁵ For example, suppose for your first test you are given as an incentive that offers an 80% chance of winning \$52. You then are told you can guarantee winning this lottery by having a second COVID-19 test in 8-months. This is preferable to a \$10 cash payment (i.e., the cost of the insurance against losing an 80:20 bet on \$52) in 8-months. To low-income persons, delivering an attractive lottery incentive for baseline testing and then letting persons insure this lottery with repeat testing may better encourage retesting by giving peace-of-mind and relieving them

of worrisome distractions about money that they may already face. We will construct two incentives for this factor: (i) a baseline incentive offering a 90% chance of \$60; (ii) a repeat financial incentive. For (ii) Group 1 receives insurance on winning the baseline incentive; Group 2 receives a lottery incentive offering a 1 in 25 chance of winning \$150. The expected reward for both Group 1 and 2 for having completed both baseline and retest is \$60 (i.e., program costs are the same). In prior work, we've shown that insuring against losing a lottery was more effective than cash payments in the cost of insurance. Here we explore if this also holds true against low-probability and high-reward lotteries for which people may be optimistic about winning.

Messaging and incentives may interact. For example, thinking about the safety of your family after a family-framed message may make insuring against losing a lottery more attractive than another risk lottery.

6.1.2 ADMINISTRATION AND/OR DOSING

Clinical research coordinators will be blinded to the participant's condition. Participants will receive information on the intervention arm as part of the initial recruitment phone call and will also receive a reminder at the time of initial test visit. This will be provided as either a sealed envelope or email/text (based on participant preference) with test return instructions and information on the incentive they will be receiving. Lotteries will be played and incentives paid at the time of Wave 2 retesting.

6.2 FIDELITY

6.2.1 INTERVENTIONIST TRAINING AND TRACKING

All recruitment callers will be trained on the randomization process and the relevant scripts household members should receive depending on intervention arm assignment. CRCs are blinded to intervention assignment; site monitors will cross check intervention assignment and ensure participants are getting correct reminder instructions.

6.3 MEASURES TO MINIMIZE BIAS: RANDOMIZATION AND BLINDING

Randomization will occur at the beginning of the study using the following steps:

NIH Protocol Template for Behavioral and Social Sciences Research Involving Humans

- We will receive a list of 6,222 names from AltaMed Health Services (3074 in the “far” group and 3148 in the “near” group; “far”/“near” based on further/nearer than the median distance of LA AltaMed patient zip codes from the testing site’s zip code).
 - Using this list, The Henne Group will reach out to these participants asking if they would like to participate in the study and have a child in the household.
 - Each household will be assigned a study ID; each participant will have a Study ID number as well as a medical record number (for patients only) from AltaMed to incorporate into the EHR.
 - A list of eligible participants will be available in our HIPAA compliant version of REDCap with their name, research ID and script option (4 options- 2 for messaging/ 2 for financial incentives)
 - Using the randomization feature in REDCap, we will be able to randomize the scripts that each participant will receive.
- Onsite Clinical research coordinators will be blinded to the participant’s condition.

6.4 STUDY INTERVENTION/EXPERIMENTAL MANIPULATION ADHERENCE

Participants adherence to Wave 2 retesting will be tracked via REDcap.

6.5 CONCOMITANT THERAPY

Not applicable

6.5.1 RESCUE THERAPY

N/A.

7 STUDY INTERVENTION/EXPERIMENTAL MANIPULATION DISCONTINUATION AND PARTICIPANT DISCONTINUATION/WITHDRAWAL

7.1 DISCONTINUATION OF STUDY INTERVENTION/EXPERIMENTAL MANIPULATION

Participants who decline testing initially will be offered an exit survey which will ask them for reasons for declining. We will longitudinally follow the initial cohort that completed baseline survey (including people who declined testing in wave 1) and offer an additional wave of testing 6 months after the first wave.

Participants can choose to withdraw from the study at any time, and this will be documented in their REDCap record. When a subject discontinues Wave 2 retesting but not from the study, remaining study procedures (data analysis) will be completed as indicated by the study protocol.

7.2 PARTICIPANT DISCONTINUATION/WITHDRAWAL FROM THE STUDY

Participants are free to withdraw from participation in the study at any time upon request. The reason for participant discontinuation or withdrawal from the study will be recorded in REDCap. Subjects who sign the informed consent form and are randomized but do not receive the study intervention may be replaced.

[figure not shown]
7.3 LOST TO FOLLOW-UP

A participant will be considered lost to follow-up if he or she fails to respond to request for Wave 2 retesting after at least 3 attempts. Should the participant continue to be unreachable, he or she will be considered to have withdrawn from the study with a primary reason of lost to follow-up.

8 STUDY ASSESSMENTS AND PROCEDURES

8.1 ENDPOINT AND OTHER NON-SAFETY ASSESSMENTS

Households who are interested in participating will be assigned a household ID, and one adult from each household will complete the study survey questions. Household members interested in testing will then be assigned a unique Study ID and be scheduled for a testing appointment at a date and time convenient for them. Participants will be called with antibody test results within 5-7 days of initial test. Six months following initial test, participants will be asked to come in for Wave 2 retesting, where lotteries will be played and incentives realized. Participants will be called with antibody test results within 5-7 days of second test. All decisions related to participation and the scheduled appointment times will be documented within REDCap.

8.2 SAFETY ASSESSMENTS

Because this study involves COVID-19 serology testing involving only a skin prick (FDA approved Tasso device) to collect the sample, we do not anticipate any adverse events for participants. Unanticipated Problems that are unexpected, related or possibly related to this research (including anywhere there is a reasonable possibility that the incident or outcome may have been caused or associated with the study) and that suggests that the research places patients at greater risk of harm than was previously known or recognized will be thoroughly and promptly investigated.

8.3 ADVERSE EVENTS AND SERIOUS ADVERSE EVENTS

8.3.1 DEFINITION OF ADVERSE EVENTS

Because this study involves COVID-19 serology testing involving only a skin prick (FDA approved Tasso device) to collect the sample, we do not anticipate any serious adverse events for participants and therefore SAE reporting is not applicable.

8.3.2 DEFINITION OF SERIOUS ADVERSE EVENTS

Because this study involves COVID-19 serology testing involving only a skin prick (FDA approved Tasso device) to collect the sample, we do not anticipate any serious adverse events for participants and therefore SAE reporting is not applicable.

8.3.3 CLASSIFICATION OF AN ADVERSE EVENT

8.3.3.1 SEVERITY OF EVENT

Because this study involves COVID-19 serology testing involving only a skin prick (FDA approved Tasso device) to collect the sample, we do not anticipate any serious adverse events for participants and therefore SAE reporting is not applicable.

8.3.3.2 RELATIONSHIP TO STUDY INTERVENTION/EXPERIMENTAL MANIPULATION

Not applicable

8.3.3.3 EXPECTEDNESS

Because this study involves COVID-19 serology testing involving only a skin prick (FDA approved Tasso device) to collect the sample, we do not anticipate any adverse events for participants.

8.3.4 TIME PERIOD AND FREQUENCY FOR EVENT ASSESSMENT AND FOLLOW-UP

Not applicable

8.3.5 ADVERSE EVENT REPORTING

Because this study involves COVID-19 serology testing involving only a skin prick (FDA approved Tasso device) to collect the sample, we do not anticipate any adverse events for participants.

8.3.6 SERIOUS ADVERSE EVENT REPORTING

Because this study involves COVID-19 serology testing involving only a skin prick (FDA approved Tasso device) to collect the sample, we do not anticipate any serious adverse events for participants.

8.3.7 REPORTING EVENTS TO PARTICIPANTS

Not applicable

8.3.8 EVENTS OF SPECIAL INTEREST

Not applicable

8.3.9 REPORTING OF PREGNANCY

Not applicable

8.4 UNANTICIPATED PROBLEMS

8.4.1 DEFINITION OF UNANTICIPATED PROBLEMS

This protocol uses the definition of Unanticipated Problems as defined by the Office for Human Research Protections (OHRP). OHRP considers unanticipated problems involving risks to participants or others to include, in general, any incident, experience, or outcome that meets all of the following criteria:

- Unexpected in terms of nature, severity, or frequency given (a) the research procedures that are described in the protocol-related documents, such as the Institutional Review Board (IRB)-approved research protocol and informed consent document; and (b) the characteristics of the participant population being studied;
- Related or possibly related to participation in the research (“possibly related” means there is a reasonable possibility that the incident, experience, or outcome may have been caused by the procedures involved in the research); and
- Suggests that the research places participants or others at a greater risk of harm (including physical, psychological, economic, or social harm) than was previously known or recognized.]

8.4.2 UNANTICIPATED PROBLEMS REPORTING

Unanticipated Problems that are unexpected, related or possibly related to this research (including anywhere there is a reasonable possibility that the incident or outcome may have been caused or associated with the study) and that suggests that the research places clinicians or patients at greater risk of harm than was previously known or recognized will be thoroughly and promptly investigated. The Unanticipated Problem will be investigated, formally written down with a corrective plan and measures to prevent reoccurrence. This report will be shared with the NIA Program Officer within 48 hours of study’s knowledge of the problem.

8.4.3 REPORTING UNANTICIPATED PROBLEMS TO PARTICIPANTS

Not applicable

9 STATISTICAL CONSIDERATIONS

[figure not shown]
9.1 STATISTICAL HYPOTHESES

The figure below provides a conceptual diagram for thinking about what factors may influence testing take-up and retesting. Testing take-up would depend on several factors, including prior beliefs about infection, health literacy, information networks, health conditions, demographics and socio-economics. We have the following hypothesis based on analysis of literature on testing for HIV and Hepatitis as well as preliminary analysis of data from our prior study:

Hypothesis 1: Those who believe that they have been infected in the past would be more likely agree to testing to confirm that they have antibodies and potential immunity; **Hypothesis 2:** People with poor health literacy will be less likely to agree to testing as they might find it daunting to understand what the test does and how to interpret results; **Hypothesis 3:** Those who are risk averse would be more likely to agree to testing as it reduces uncertainty about serostatus; **Hypothesis 4:** Those with preexisting health conditions would be more likely to agree to testing as they face higher risks from COVID-19 and thus have more to gain from learning serostatus; **Hypothesis 5:** Minorities and those in lower socio-

economic strata would be less likely to agree to testing due to fear of discrimination, lack of trust in health care/research, poor past experience, and perception of being at low risk of infection. We also generate hypotheses for facilitators to retesting (r) relative to those who take a first test **Hypothesis 1r:** Persons who practice low COVID-19 mitigation, exhibit risk-seeking and have high exposure risk may respond to a lottery retest incentive. **Hypothesis 2r:** Those persons with low income, unemployed, or have high stress or anxiety may respond most to insurance of incentives. **Hypothesis 3r:** Persons who are sero+ at baseline will be less likely to return for a retest. **Hypothesis 4r:** Lottery insurance and family messaging will induce higher retesting rates. Hypotheses 1-5 are covariates that may affect agreeing to the test. Hypotheses 1r and 2r refer to heterogeneity of treatment effects for retesting, while 3r and 4r are main effects on retesting.

Conceptual diagram

9.2 SAMPLE SIZE DETERMINATION

We will recruit a cohort of 2,160 people (540 families), and stratify into 3 subgroups based on predictors of commitment to participation in testing programs. Randomization will be clustered by family. Sub-group membership will be based on the mean household survey response to the survey component. For the purposes of power analyses, we assume high Intra Cluster Correlation within family on uptake of repeat testing (>0.90).

Stratified Allocation Plan and Power Analysis (540 households, 2160 individuals)		
	Control	Intervention
Stratification	# households	# households
HTE Subgroup 1	60	60
HTE Subgroup 2	60	60

HTE Subgroup 3	60	60
% Seropositive in Baseline Test	10%	10%
Total Households Per Arm	180	180
Projected Average Treatment Effect Size	Reference Group	Reference+10%
Minimum Detectable Effect Size Compared to Controls (H4r)	±3%	
Detectable 3-subgroup HTE and Seropositivity (H1r, H2r, H3r)	±7%	

Assuming a similar effect size to prior studies in similar populations, we expect a 10 percentage point difference in repeat testing adherence between intervention and control groups. With 540 households, we are powered to detect as little as 3 percentage point difference between interventions and controls in the 540 households we will enroll. To assess heterogeneity of treatment effects (THE), there is more than 80% power to detect a between-subgroup difference of 7 percentage points, assuming 180 households in each sub-group.

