1 PROTOCOL SUMMARY

1.1 SYNOPSIS

Title:	Use of Behavioral Economics in Repeat SARS-CoV-2 Antibody Testing in Disadvantaged Communities
Grant Number:	3R33AG057395-04S1
Study Description:	Uptake of SARS-CoV-2 testing in underserved populations is subject to barriers related to resources and behaviors that may differ within communities and even households. Testing for SARS-CoV-2 antibodies in underserved populations can play an important strategic role. It is important to understand barriers and actionable facilitators of testing in underserved populations to address those most in need.
Objectives* :	Primary Objective: This project aims to evaluate the effectiveness of risk-based messaging and incentives that promote repeated testing for SARS-CoV-2 antibodies. Secondary Objectives: To understand social and behavioral determinants of COVID-19 testing and variations within sub-groups of this population.
Endpoints* :	Primary Endpoint: Characterize barriers to access, bias, risk attitude and incentive preferences through outreach and survey responses. Secondary Endpoints: Identify groups that may partition facilitators to testing into minimal and maximal effectiveness. Evaluate interventions and their heterogeneous treatment effects on social determinants and address barriers to test participation in a randomized trial.
Study Population:	2,160 individuals (540 families) from the largest Federally Qualified Health Center (AltaMed Health) in Los Angeles, California.
Phase* or Stage:	Stage III clinical trial
Description of Sites/Facilities Enrolling Participants:	AltaMed Health Services is one of the largest qualified health centers in the United States. The Commerce clinic site will be a participating site enrolling participants. The study does not intend to include sites outside of the United States.
Description of Study Intervention/Experimental Manipulation:	Using a random sample of households, we will recruit participants to conduct a randomized 2 x 2 (Messaging x Incentive) factorial experiment, in which participants complete a comprehensive set of social and behavioral surveys to identify determinants of commitment to testing.
Study Duration* :	24 months
Participant Duration:	12 months

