4.1 OVERALL DESIGN

Social determinants need to be understood in the context of actionable facilitators (things COVID-19 policymakers can do) to encourage repeat testing. We will study two types of facilitators (messaging and financial incentives) and evaluate the heterogeneity of treatment response based on the characteristics of those tested. We will conduct a 2 x 2 (messaging x financial incentive) factorial design (Aim 3) that stratifies on social and behavioral determinants (Aim 2) collected as part of an initial survey (Aim 1). We have been studying ways to identify powerful incentives for repeated health behaviors. We have found that providing at-risk incentives that can be insured with repeat health behavior outperforms direct cash payments of the same expected value. Individuals were 70% more likely to return to a health screening when insuring against losing a baseline incentive than they were when paid cash ($p < 0.01$).⁴ In addition, in a recent study we showed that disadvantaged patients at a federally-qualified health center were more likely to repeat a health behavior twice each week over 12 weeks when repetition

was insuring against losing a weekly incentive than if they were paid equivalently in cash (see Figure 1; $p < 0.05$).

5

Figure 1. Insurance (loss protection) vs. cash (control) incentive for repeat health behavior among disadvantaged persons (N = 151)

2 x 2 Stratified Randomization

Messaging (Factor 1): We will develop simple messaging that frames the decision to test in terms of either: (i) family risk, or, (ii) personal risk. These methods will be piloted, but will be of the form "Antibody testing will help you understand your family's risk of getting COVID-19"; and, "Antibody testing will help you understand your risk of getting COVID-19". Family risk framing may engender concern for loved ones. It may also make it easier to mentally simulate family burdens with COVID-19 such as knowing how several people in the family becoming sick could adversely affect the lives of everyone in the family. We hypothesize that the family framing will result in greater uptake of testing and greater repeat testing.

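### The section 9.2 power table does not describe the 2x2 factorial, and its 3-point and 7-point detectable effects do not follow from the stated ICC

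*Combined protocol and SAP*

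**What the plan says.** The synopsis describes a "randomized 2 x 2 (Messaging x Incentive) factorial experiment", and section 6.3 lists four scripts, two for messaging and two for incentives. Section 4.1 makes both levels of each factor active: family-risk or personal-risk message, and insurance of the baseline lottery or a new 1-in-25 lottery.

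Section 9.2 plans 540 households and 2,160 people and states that "Randomization will be clustered by family", with an intra-family correlation above 0.90 for repeat testing. Its table, titled for 540 households, has two columns, Control and Intervention. Each holds 60 households in each of three subgroups, and the row "Total Households Per Arm" gives 180 and 180. The table assigns ±3% to H4r (lottery insurance and family messaging) and ±7% to H1r, H2r and H3r.

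The text below it projects a 10-point effect and says "we are powered to detect as little as 3 percentage point difference between interventions and controls in the 540 households we will enroll". It then claims more than 80% power for a 7-point between-subgroup difference, "assuming 180 households in each sub-group".

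The analysis in section 9.4.1 uses factor levels and cells. Model 4a takes lottery and personal messaging as references. Model 4b compares three cells with the personal/lottery cell.

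**The concern.** A table built on arms of 180 fits two arms or three, not four cells. A reader therefore cannot tell which contrast the detectable effects refer to, or how many households inform it. The ICC is the more serious matter: with randomization by family and a correlation above 0.90, four relatives carry little more information than one, and 3 points looks far too small for 540 households.

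This is the trial's only sample-size justification. Taken at face value, a detectable difference of 3 points leaves a wide margin below the projected 10. A null result could then be read as excluding effects that the trial had little chance of seeing. The same applies to the 7-point figure and the heterogeneity hypotheses.

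**Working it through.** **Inputs.** From section 9.2: 540 households, 2,160 people (2,160/540 = 4 per household), ICC above 0.90 (0.90 used, which favours the plan), and 80% power (stated only for the heterogeneity claim). Assumed because the plan is silent: two-sided 5%, equal allocation, a range of retest rates, and no loss between tests.

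**Counts.** 540/4 = 135 per cell; 540/2 = 270 per factor level. The table's two columns give 2 × 180 = 360. A third column would give 3 × 180 = 540, which is a three-arm layout.

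**Formula.** Design effect = 1 + (4 − 1) × 0.90 = 3.7. Effective n per group = households × 4/3.7: 291.9 for 270, 194.6 for 180, 145.9 for 135, 97.3 for 90. Detectable difference = 2.80 × √[p(1−p)(1/n₁ + 1/n₂)], with 2.80 = 1.96 + 0.84. Example, 270 v 270 at p = 0.5: 2.80 × √(0.25 × 2/291.9) = 0.116.

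**Attempt to reproduce 3 points, and the contrasts the trial makes** (percentage points, ICC 0.90):

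| Contrast (households) | p = 50% | p = 20 or 80% | p = 10 or 90% |
|---|---|---|---|
| 180 v 180 (table as read) | 14.2 | 11.4 | 8.5 |
| 180 v 360 (if a third arm of 180) | 12.3 | 9.8 | 7.4 |
| 270 v 270 (factor main effect) | 11.6 | 9.3 | 7.0 |
| 135 v 135 (cell contrast) | 16.4 | 13.1 | 9.8 |

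No layout gives 3. Solving for the rate at 270 v 270: p(1−p) = (0.03/2.80)² × 291.9/2 = 0.0167, so p is about 1.7% (or, by symmetry, about 98.3%). Power for a 3-point difference at 270 v 270 is roughly 11% to 21% for reference rates from 10% to 80%.

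**Setting the ICC to 0.** 270 v 270 (n = 1,080 per level) gives 6.0 / 4.8 / 3.6 points at the same rates and reaches 3 points at a rate of about 6.6%.

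**The 7-point figure.** There are two readings:

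- Two subgroups of 180 compared directly: 14.2 / 11.4 / 8.5 points.
- Difference in treatment effect between two subgroups of 180, each split 90 v 90: √2 × (20.08 / 16.07 / 12.05) = 28.4 / 22.7 / 17.0 points.

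Neither reading fits H3r, which compares individuals by baseline serostatus.

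**The projected 10-point effect.** Pooled normal approximation, 270 v 270. At 50% v 60% the null SE is √(2 × 0.55 × 0.45/291.9) = 0.0412 and the alternative SE is √[(0.25 + 0.24)/291.9] = 0.0410. Power = Φ[(0.10 − 1.96 × 0.0412)/0.0410] = 68%. The same calculation gives 72% at a 30% reference rate and about 92% at 10% or 80%.

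**The case against.** Several stronger readings are tempting, and the documents do not support them.

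- **The plan has lost 180 households.** The table adds to 360 under a 540 title, and to 120 per subgroup where the text has 180. But the table was read from a PDF and is visibly broken. One lost column of 60/60/60 restores both totals, so these sums cannot be held against the plan. What stands is that two or three arms of 180 are not four cells.
- **There is no control, so the contrast does not exist.** The protocol uses the word loosely: the Figure 1 caption in section 4.1 calls a cash incentive the control, and the power table labels the control column as the reference group. H4r is a contrast that Models 4a and 4b estimate. It is poorly labelled, not absent.
- **The 3 points came from 180 v 180.** The text ties the figure to all 540 households, so its origin cannot be shown.
- **3 points fails even without clustering.** It fails at rates from 10% to 90%, but not near 5% to 7%, and the plan states no rate.
- **The trial is underpowered for its projected effect.** At a 10% or 80% reference rate, power for 10 points at 270 v 270 is about 92%. It drops below 80% only towards the middle of the range.

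It is also fair to say that the heterogeneity shortfall is much smaller on the direct-comparison reading (8.5 to 14.2 against 7), and that the 135 and 270 counts depend on an allocation ratio that the plan does not give. None of this rescues 3 points at an ICC of 0.90.

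**Conclusion.** The point stands in two parts. The table's layout does not match the 2x2 factorial: no reading of it yields 135 per cell or 270 per factor level. Separately, and more important, the stated detectable effects do not follow from the stated ICC under any layout. For a factor main effect the detectable difference is about 7 to 12 points, not 3, over retest rates from 10% to 90%; for a cell contrast it is about 10 to 16. To detect 3 points at ICC 0.90, the retest rate would have to be below about 2% (or above about 98%). The 7-point figure is also too small on both readings over the rates shown.

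These results assume two-sided 5%, 80% power, equal allocation, four people in every household and no attrition. They are for a simple difference in retest proportions; Model 4a estimates time-by-factor interactions, which need their own calculation. An ICC above 0.90, or loss between tests, would make the figures worse. Correcting the household counts alone would not repair the claim.

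**What to change.** 1. Relabel the table by factor level (lottery v insurance, personal v family) and by cell, with the planned allocation ratio and the resulting household counts. Any counts by subgroup should be marked as assumptions, because section 9.4.5 leaves the stratification thresholds to be set after a week of testing.
2. Withdraw the 3-point and 7-point figures.
3. Restate the detectable differences for the Model 4a, Model 4b and heterogeneity contrasts at the stated ICC, giving alpha, sidedness, power and an assumed retest rate, preferably over a range of rates. Say whether the heterogeneity figure is a subgroup comparison or a difference in treatment effects, and treat H3r separately.
4. Report power for the projected 10-point effect on the same basis.

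The cost is a rewritten section 9.2 with less favourable figures. Enrolment and the analysis models do not change.
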